9.2 Statistical Analysis Plan

Descriptive statistics will be used. All data will be summarized by dose cohort, dose expansion and overall subject population.

9.3 Safety

The adverse events observed will be summarized as frequency, proportion of patients, and exact 95% confidence interval for proportion, categorized by type (organ affected or laboratory determination), severity by CTCAE v4.03 and nadir or maximum values for the laboratory measures), time of onset (i.e., course number), duration, and reversibility or outcome. Tables will be created to summarize these toxicities by dose and course. The secondary endpoint is safety and toxicity. A treatment limiting toxicity (TLT) will be defined as a treatment related grade 3-4 non-hematologic toxicity and will require dose de-escalation. If a TLT does not resolve within 5 days, is not responsive to management, or occurs at the lowest dose level (1 million IU IL-2) after de-escalation then that patient will be removed from trial and the therapy will be deemed intolerable. Therapy will be deemed safe and tolerable if no greater than 33% of patients find the treatment intolerable.

9.4 Efficacy

As an exploratory endpoint, all responses will be reported using RECIST 1.1 definitions [58]. Because of the potential heterogeneity of the patients, all results will be considered preliminary and hypothesis generating for future studies. Response rate among will be summarized by exact binomial confidence intervals. Disease free survival will be summarized with Kaplan-Meier plots to describe the outcome of patients treated on this protocol. The median DFS time will be estimated using standard life table methods.

9.5 Subject Course

Information regarding the subject's course such as completing the study treatment, dose delays, premature discontinuation and major protocol violation will be captured in electronic CRFs.

9.6 Correlative Laboratory Markers

Correlative biomarker endpoints are exploratory and hypothesis generating. Descriptive statistics will be applied to characterize differences within a given patient pre-treatment to post-treatment and across the cohort of patients. Changes in the correlative endpoints will be evaluated using a two-tailed paired student's T-test. To provide a preliminary estimate of the predictive or prognostic value of the various correlative endpoints for DFS we will be using multiple regression analysis with ordinal category for response (generalized linear models) or time to event (proportional hazards survival analysis) as the outcome. We will compute descriptive statistics (mean, standard deviation, median, minimum, and maximum) for mutational load and the immune-related variables (e.g., TILs, Tregs, CD8/Treg ratio, PDL-1, IDO, CTLA-4, PD-1, and immune gene signatures) by tumor type and in the sample as a whole. We will assess the association between mutational load, each immune-related variable, and clinical outcomes by computing Pearson or Spearman correlation coefficients with 95% confidence intervals, as well as using graphical methods to determine whether the associations are generally linear or whether another functional form fits the data better. We will have at least 80% power to detect a moderate correlation of 0.4 at the 0.05 level (2-sided). We may also develop multiple regression models to further explore the relationship between clinical outcomes and correlative markers.

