7.1.4.3 Evaluation of Best Overall Response

The best overall response is the best response recorded from the start of the treatment until disease progression/recurrence (taking as reference for PD the smallest measurements recorded

since the treatment started). In general, the patient's best response assignment will depend on the achievement of both measurement and confirmation criteria.

Table 12. Best Overall Response Evaluation

Target Lesion	New Lesion	Overall Response
CR	No	CR
PR	No	PR
SD	No	SD
PD	Yes or No	PD

Patients with a global deterioration of health status requiring discontinuation of treatment without objective evidence of disease progression at that time should be classified as having "symptomatic deterioration". Every effort should be made to document the objective progression even after discontinuation of treatment.

In some circumstances it may be difficult to distinguish residual disease from normal tissue.

When the evaluation of complete response depends on this determination, it is recommended that the residual lesion be investigated (fine needle aspirate/biopsy) to confirm the complete response status.

Duration of Overall Response

The duration of overall response is measured from the time measurement criteria are met for CR or PR (whichever status is recorded first) until the first date that recurrence or PD is objectively documented, taking as reference for PD the smallest measurements recorded since the treatment started.

Duration of Stable Disease

SD is measured from the start of the treatment until the criteria for disease progression are met, taking as reference the smallest measurements recorded since the treatment started.

The clinical relevance of the duration of SD varies for different tumor types and grades.

Therefore, it is highly recommended that the protocol specify the minimal time interval required between two measurements for determination of SD. This time interval should take into account the expected clinical benefit that such a status may bring to the population under study.

Disease Control Rate (DCR)

DCR is defined as the percentage of patients that achieve an objective tumor response or stable disease to therapy.

Progression-Free Survival (PFS)

PFS is defined as the duration of time from start of treatment to time of progression or death, whichever occurs first.

Abscopal Response Rate (ARR)

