8.0 CORRELATIVE SCIENCE (Translational Research)

8.1 Rationale

One of the major shortcomings of immunotherapy trials has been the lack of in-depth correlative studies to help identify the mechanism of action and resistance, identify biomarkers of response, and provide a foundation for further improving these approaches. To address this, we plan to perform in depth immunological analysis of mandatory serial patient blood and tumor samples. Tumor biopsies will be obtained pre-treatment and during the final intralesional needle placement for IL-2 delivery. Blood samples will be obtained pre-treatment, after the final dose on intralesional IL-2 and at the first response assessment time point at 6 weeks. We will evaluate immunologic changes systemically and in the tumor microenvironment within patient's pre to post therapy and across the cohort of patients to identify predictive biomarkers and elucidate the mechanistic immunologic effects of therapy and therapy resistance. We will examine putative biomarkers of response to checkpoint immunotherapy such as PD-L1 expression, mutational load, and TILs.

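### Section 9.6 correlates markers with a censored outcome and sets no landmark for on-treatment samples, so PFS associations can be weakened and some can be false

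*Combined protocol and SAP*

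**What the plan says.** Section 9.6 describes two ways of relating markers to outcome.

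- Mutational load and each immune variable are to be related to "clinical outcomes by computing Pearson or Spearman correlation coefficients with 95% confidence intervals". No outcome is named, and nothing is said about censored times.
- To estimate the "predictive or prognostic value of the various correlative endpoints for DFS", it plans "multiple regression analysis with ordinal category for response (generalized linear models) or time to event (proportional hazards survival analysis) as the outcome".

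The section states that "Correlative biomarker endpoints are exploratory and hypothesis generating". It does not say which sampling time enters the models, and it gives no landmark, delayed entry or time-dependent covariate.

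The outcomes are defined in section 7.1.4.3. Abscopal response and disease control are yes/no per patient. For the time-to-event outcome, "PFS is defined as the duration of time from start of treatment to time of progression or death, whichever occurs first". Section 5.11 lets follow-up end at loss to follow-up, withdrawal of consent or study termination, so PFS can be censored. DFS appears in the abbreviation list and in 9.4 and 9.6, but no event is defined for it.

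On timing, translational objective 3 in section 3.3 correlates the serial blood and biopsy parameters with outcome, so on-treatment values are in scope. Section 8.1 places one blood draw "at the first response assessment time point at 6 weeks". The study calendar (6.1) lists research blood under Cycle 3, but its imaging footnote puts the first on-treatment scan at the end of cycle 3.

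**The concern.** Two separate problems arise if 9.6 is followed literally.

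**Censoring.** A Pearson or Spearman coefficient needs a complete outcome value. With PFS, either the censored time stands in for the event time or the censored patients are dropped. The first weakens a real association. It can also create a false one when the marker is related to how long patients were followed, for example through assay drift over the accrual period.

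**Timing of the marker.** A sample taken at the scan that reveals progression may reflect progression and not predict it. If it enters a Cox model with PFS counted from treatment start, patients who progress at that scan contribute an event together with a marker value that the event may have altered.

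At stake is translational objective 3, the search for biomarkers of response and resistance. A marker of current progression could be carried forward as a predictor, and a true predictor of PFS could look weak.

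**Working it through.** **The one figure in 9.6.** The plan claims at least 80% power for a correlation of 0.4 at two-sided 0.05. By Fisher's z, the required N = ((1.960 + 0.842)/atanh 0.4)² + 3 = (2.802/0.4236)² + 3 = 46.7, so 47. At the trial maximum of 25, power = Φ(0.4236·√22 − 1.960) = 0.51. At 46, the number implied by section 8.2 (92 biopsies/2, 138 blood samples/3), it is 0.79. This is a separate matter, but it means that there is little precision to lose at 25 patients.

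**Correlation with a censored time.** Assumptions: exponential PFS, and censoring unrelated to the marker.

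- A true Spearman of 0.46-0.48 becomes about 0.31 at 41-43% censoring. The ratio is 0.31/0.48 = 0.65 to 0.31/0.46 = 0.67, so about a third is lost.
- An underlying normal correlation of 0.40 (median PFS 4 months) gives Pearson/Spearman of 0.36/0.39 with no censoring, 0.28/0.29 at 42% and 0.22/0.22 at 62%.
- With no true effect and n = 25, both tests reject in about 5% of trials. Independent censoring therefore weakens the estimate but does not create false positives.
- If a null marker drifts with entry date (assumed correlation 0.5 with follow-up length, median PFS 12 months), Pearson rejects in 16% and Spearman in 13%, against 5% for Cox.

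**Marker measured at the scan.** Assumptions: n = 25, first scan at week 9 (three 3-week cycles), and a marker with no effect on later hazard but shifted in patients who have progressed by that scan. Median PFS is taken as 10 weeks, 17 weeks or 4 months. The 10 weeks is the 2.3 months that section 4.5.1 quotes for nivolumab in NSCLC (2.3 × 4.345 = 10.0), which is a different population. Rejection rates at nominal 0.05:

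| Assumed shift | Cox from day 1, all patients | Cox from landmark |
|---|---|---|
| none | about 0.05 | 0.03-0.06 |
| 0.5 SD | 0.08-0.14 | 0.03-0.06 |
| 1 SD | 0.19-0.42 | 0.03-0.06 |

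The spread within a row reflects the assumed median and the handling of tied events at the scan; Breslow ties give the lower values. With a median of 8 months the 1 SD figure is 0.14. At a 4-month median and 1 SD, the median hazard ratio per SD is 1.30 from day 1 and 1.00 from the landmark. In that same setting Spearman with PFS time rejects in 37% and Pearson in 17%.

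**Source of the bias.** Among patients event-free at a common sampling time, Cox from day 1 and Cox from the landmark have the same partial likelihood. The false association therefore comes from including patients whose event falls at or before the sample, and not from the day-1 origin itself.

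**Patients lost to the landmark.** The share progressing by week 9 is 1 − 2^(−9/10) = 0.46 at a 10-week median and 1 − 2^(−9/17) = 0.31 at 17 weeks. Of 25 patients, about 13 to 17 remain.

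**The case against.** Section 9.6 already contains suitable models, an ordinal model for response and proportional hazards for time to event, so the correlations are an added summary. That stands, and it limits the first problem. It does not remove it, because a weakened estimate and a valid one of the same association would appear side by side with no rule on which to read.

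A reader might infer that Pearson and Spearman are unsuitable for every outcome here. The documents do not support that. Response enters 9.6 as an ordinal category, for which Spearman is usable, and the sentence can be read to cover marker-marker pairs, where both coefficients are valid. For yes/no response, Spearman and exact Mann-Whitney agreed on significance in 99% of simulated trials (25 patients, 5 responders). The point-biserial ceiling of 0.70 at 20% responders limits the scale and is not a source of false findings.

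A reader might also infer that the plan names the scan-day sample as a predictor of PFS. It does not. This follows only from objective 3, the draw described in 8.1 and the unrestricted wording of 9.6. Mutational load and other pre-treatment markers are unaffected, and the second biopsy (cycle 2, week 3) precedes the scan. By the calendar the Cycle 3 draw could fall about three weeks before the scan. The problem at the scan thus concerns one draw whose timing is inconsistent.

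Finally, no document supports a shift of 1 SD, and the work is exploratory. Both are correct.

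**Conclusion.** The point holds as a gap in specification that can mislead. Correlating a marker with censored PFS weakens the estimate, by roughly a third at 41-43% censoring in one setting, and can give false associations when the marker is related to follow-up length. With no landmark, an on-treatment marker can show a false association with PFS if it is altered in patients who have already progressed. The illustrative error rate is 0.19-0.42 at a 1 SD shift and 0.08-0.14 at 0.5 SD.

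These figures rest on assumed medians, exponential times, assumed shifts and 9-week scans. They show direction and size and do not forecast this trial. It would go too far to say that false associations will arise: with no shift and independent censoring the error stays near 5%. Nor does the point touch the efficacy decision, which under section 9.1 rests on abscopal response. A correction is warranted because the discovery aim depends on these analyses and the remedy is standard.

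**What to change.** Amend section 9.6 as follows.

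1. For PFS, drop the correlation and report the hazard ratio (or Harrell's C) with its interval from the Cox model already planned.
2. Keep Pearson and Spearman for marker-marker pairs. For response category, use Spearman or the planned ordinal model.
3. State which sampling times enter each model. For any on-treatment marker, include only patients still progression-free after the sampling date and count PFS from that date.
4. Treat a sample drawn at the first response scan as descriptive for that scan's result.
5. Replace DFS by PFS.
6. Reconcile the time of the draw: 8.1 puts it at the first response assessment at 6 weeks, while the calendar puts that scan at the end of cycle 3.

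The cost is SAP text and routine code, with no extra samples or visits. The drawback is that about 31-46% of patients, under assumed median PFS of 17 or 10 weeks, leave the landmark analysis for a week-9 sample, so its intervals widen. Their marker values can still be reported descriptively.

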2.0 TRIAL DESIGN

Patients with advanced solid malignancies or lymphoma with progression on prior PD-1/L1 blockade will be enrolled. A total maximum of 25 patients will be enrolled.

Primary Objective: Abscopal response rate, ORR, DCR, PFS
Secondary Objective: Maximum tolerated dose (MTD), safety, and toxicity
Collateral Objectives: Immunophenotype serial tumor biopsies and blood samples

Phase I: IL-2 Dose Findin: 3+3 Design: (3-6 patient dose level, 6-18 patients total)				
	Treatment 1 dose	Treatment 2 dose	Treatment 3 dose	Treatment4 dose
Dose Level -1	1 x 10 ⁶ IU	1 x 10 ⁶ IU	1 x 10 ⁶ IU	1 x 10 ⁶ IU
Dose Level 1	3 x 10 ⁶ IU	3 x 10 ⁶ IU	3 x 10 ⁶ IU	3 x 10 ⁶ IU
Dose Level 2	3 x 10 ⁶ IU	7 x 10 ⁶ IU	7 x 10 ⁶ IU	7 x 10 ⁶ IU
Dose Level 3	3 x 10 ⁶ IU	7 x 10 ⁶ IU	15 x 10 ⁶ IU	15 x 10 ⁶ IU

Phase II: IL-2 Dose Expansion Binomial one-Stage Design (18 additional patients; analyzed with patients from MID)	

 P= 0.05, p1= 0.20, r1= 0, n1= 10, rTot=3, nTot=21, a= 0.1, power=0.8 Response will be assessed according to irRECIST and will be evaluated at the non-treatment lesions (abscopal response) 	

CT= computed tomography, DCR=disease control rate, MTD=maximum tolerated dose, ORR=objective response rate, PFS=progression free survival, RT=radiotherapy, P=pembrolizumab,

- a. Patients will be clinically evaluated prior to each cycle of pembrolizumab for the first 3 cycles and weekly during intralesional IL-2 injections, and thereafter every 3 cycles until off treatment.
- b. Laboratory evaluation will occur pre-treatment at every cycle.
- c. For response assessment, patient will have CT imaging pre-treatment and after every three cycles of pembrolizumab.

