4.11 Biomarkers

One of the major shortcomings of immunotherapy trials has been the lack of in-depth correlative studies to help identify the mechanism of action, identify biomarkers of response, and explain the mechanisms governing treatment response or failure. To address this, we plan to perform in depth immunological analysis of patient blood and tumor samples. This study incorporates serial tissues samples pre- treatment, during therapy, and at progression. The design of this study allows us to compare immune mechanisms pre- to post-therapy.

Tumor PD-L1 expression has been linked to response rates of PD-1 checkpoint blockade[7]. Pre-clinical data suggests that radiotherapy may upregulate intratumoral PD-L1 expression[52] but little is known about the dose response of these effects. Additionally, little is known about how the pattern of expression (i.e., tumor cells vs. infiltrating immune cells) affects response. Data presented at ASCO and SITC indicate that durvalumab monotherapy response rates in NSCLC are 27% in PD-L1 positive tumors and 5% in PD-L1 negative tumors. TILs and a T-cell inflamed phenotype have been linked with response to CTLA-4 checkpoint blockade in melanoma [53, 54]. Exclusion of T-cells in the tumor microenvironment has also been linked with lack of response to checkpoint inhibition [55] with down-regulation of CCL4 mediated dendritic cell recruitment as one potential mechanism [55]. RT has been demonstrated to induce TILs[56] and may potentially overcome this mechanism of resistance to checkpoint blockade. Our unpublished data suggests that RT can induce CCL4 expression and increase TILs. Likewise, IL-2 may expand intratumoral T-cells helping to circumvent the mechanisms of checkpoint blockade resistance.

Mutational burden and antigenic load are thought to represent a surrogate for tumor antigenicity and have been linked with response to checkpoint blockade in NSCLC [57]. Whether mutational load is a true indicator of tumor antigenicity and how this correlates with response to this combinatorial approach is unknown.

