- g. CT or MRI at pre-treatment and q 3 cycles until progression (e.g., at the end of cycle 3, ,6, 9, etc.).
- h. See the correlative study section for detailed information (Section 8.0)
- i. Biopsy: Tumor biopsies will be obtained prior to cycle 1 treatment and during the final intralesional needle placement for IL-2 delivery (Cycle 2 Week 3).
- j. Follow-up: patients on active treatment at 12 months may continue to receive pembrolizumab, but will revert to SOC management and be labeled in "follow-up". At this time only PFS and long-term toxicity data will be collected every 3 months as part of routine SOC management.
- k. Research blood to be drawn prior to starting therapy for cycle 1 and 2. After Cycle 3 research blood to be drawn at cycle 6 then every 6 cycles thereafter.
- l. Stool sample will be collected from patients before initiation of treatment

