8.2 Study Design and Methodology

Details of correlative study sample collection, preparation, and storage are outlined in

Appendix 3. For translational studies tumor tissue will be obtained pre- and post- treatment and peripheral blood will be obtained pre-treatment and at two time points post-treatment from each patient. Thus, a total maximum of 92 fresh tumor biopsies and 138 blood samples will be obtained for this study. We have extensive expertise in all of the techniques described at the UC Davis Laboratory of Tumor Immunology and immune monitoring core.

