9.0 DATA AND STATISTICAL ANALYSIS PLAN

9.1 Sample Size

This is a phase I/II study that will enroll patients with an advanced solid malignancy, or lymphoma to determine if this regimen converts patients with resistance to PD-1/PD-L1 blockade into responders as determined by abscopal response rate (defined as response rate at lesions not treated with RT + IL-2) using irRECIST as well as ORR, DCR, and PFS using RECIST 1.1.

The phase I dose escalation will employ a standard 3 + 3 design with a goal of determining the MTD through DLT assessment. With three dose escalation levels this arm will recruit up to 18 patients.

The Phase II dose expansion will employ a binomial one stage design which will allow us to evaluate if this therapy can convert those resistant to PD-1/PD-L1 blockade into responders. Response will be assessed according to RECIST and will be evaluated at the non-treatment lesions (abscopal response). In order to minimize the required patient numbers, the 3 patients enrolled at the MTD will be included in the phase II efficacy evaluation. We have chosen a threshold of 5% response as not worthy of further evaluation (p0) and a threshold of 20% as worthy of further evaluation in a larger trial (p1). The trial will enroll a total of 21 patients including the three patients treated at the MTD in the phase I (ntot) and must have greater than 3 responders (rtot) for this regimen to be deemed worthy of further evaluation. This design provides a type I error rate of 0.1 and power of 0.82. This trial design will enroll a total maximum of 25 evaluable patients

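### Section 9.6 claims at least 80% power for a correlation of 0.4, which needs 46–47 patients; at the cap of 25 the power is about 51–53%

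*Combined protocol and SAP*

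**What the plan says.** Section 9.6 plans Pearson or Spearman coefficients, with 95% confidence intervals, relating mutational load, each immune variable and clinical outcome. It then states: "We will have at least 80% power to detect a moderate correlation of 0.4 at the 0.05 level (2-sided". No number of patients is attached to that sentence. The same section labels the correlative endpoints as exploratory.

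The trial size is given elsewhere. Section 2.0 says "A total maximum of 25 patients will be enrolled", section 9.1 says "This trial design will enroll a total maximum of 25 evaluable patients", and the summary table in section 1.0 also gives 25 as the maximum.

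Section 8.2 specifies tissue before and after treatment (two biopsies) and blood before treatment and at two later times (three draws) for each patient. It concludes that "a total maximum of 92 fresh tumor biopsies and 138 blood samples will be obtained for this study".

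**The concern.** The sentence fixes the effect size, the significance level, the sidedness and the power, so the required sample size follows from it. That sample size is nearly twice the enrolment cap.

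The risk lies in how null results will be read. Told that power is at least 80%, a reader would take a non-significant marker as fair evidence against a correlation of 0.4. At 25 patients a true correlation of 0.4 would be missed about half the time. Relating immune parameters to clinical outcome is a stated translational objective (section 3.3), and section 8.1 makes the serial biopsies and blood draws mandatory. Those weighing that burden on patients should see the effect that the trial can actually detect.

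**Working it through.** **Inputs.** Correlation 0.4 against a null of 0, two-sided 0.05 and power 0.80 (section 9.6). Maximum 25 patients (sections 1.0, 2.0, 9.1). Phase II efficacy number 21 (section 9.1), used here only as an illustration of fewer analysable patients. Sample totals 92 and 138, with two biopsies and three draws per patient (section 8.2). Bivariate normality is assumed for Pearson.

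**1. Sample size at which the plan's figure holds.** Fisher z:

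n = ((1.960 + 0.842) / atanh(0.4))² + 3 = (2.802 / 0.4236)² + 3 = 46.73, so 47.

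As a second method, take the t-test of r under bivariate normality. Given V, distributed as chi-square with n − 1 degrees of freedom, the statistic is noncentral t with n − 2 degrees of freedom and noncentrality [ρ/√(1 − ρ²)]·√V. Power is the average over V. This gives 0.793 at n = 45 and 0.802 at n = 46. The stated 80% is therefore correct for 46–47 patients.

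**2. Power at the documented sizes.** Fisher z: power = Φ(0.4236·√(n − 3) − 1.960). At n = 25 this is Φ(0.4236 × 4.690 − 1.960) = Φ(0.027) = 0.511.

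| n | Fisher z | Exact |
|---|---|---|
| 21 (illustrative) | 0.44 | 0.45 |
| 25 (cap) | 0.511 | 0.526 |
| 36 (18 + 18, above the cap) | 0.682 | 0.694 |
| 46 | 0.793 | 0.802 |
| 47 | 0.802 | 0.811 |

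**3. Other readings at n = 25.** Treating the regressor as fixed gives 0.552. A one-sided 0.05 test, which is not what 9.6 states, gives 0.634–0.652. Simulated Spearman power is 0.47 when the underlying Pearson correlation is 0.4, and 0.50 when the population Spearman correlation is 0.4. None comes near 0.80.

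**4. Correlation detectable with 80% power.** r = tanh(2.802/√(n − 3)). At n = 25 this is tanh(0.597) = 0.535 (exact method 0.526). At n = 21 it is 0.579 (exact 0.567).

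**5. Interval width at n = 25.** The limits are tanh(atanh(r) ± 1.960/√22). An observed r of 0.4 gives 0.006 to 0.687. An observed r of 0 gives −0.395 to 0.395.

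**6. Sample totals.** 92/2 = 46 and 138/3 = 46, against a cap of 25. At two biopsies each, 25 patients give 50.

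The blood total cannot be rescaled in the same way. Section 8.1 describes three draws, beginning "Blood samples will be obtained pre-treatment, after the final dose on intralesional IL-2" and ending at the first response assessment. Footnote k of the study calendar goes further: "After Cycle 3 research blood to be drawn at cycle 6 then every 6 cycles thereafter". For 25 patients, three draws give 75. The calendar as it reads here shows four draws through Cycle 3 (100 samples) and five through Cycle 6 (125). The calendar counts depend on column alignment in a table extracted from PDF and are indicative only.

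**The case against.** The strongest reply concerns weight. Section 9.6 calls these endpoints exploratory, section 9.4 treats all results as preliminary, and no decision rule, error rate or patient number depends on the power sentence. The planned intervals will show the imprecision. All of that stands and keeps the point modest, but it does not make the stated figure right.

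A second reply is that 25 is not fully settled. Section 2.0 caps patients enrolled, whereas section 9.1 caps evaluable patients. Section 9.1 also allows up to 18 in phase I, and section 2.0 adds 18 in phase II, making 36. The counts do need reconciling, but even at 36 the power is only 0.68–0.69.

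A third is that 21 is the efficacy number and has no direct link to how many patients will have usable samples. That is fair, and it serves here only as an illustration. Appendix 3 has patients being offered the correlative studies with consent, so the usable number could be lower still.

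Finally, the mention of tissue at progression in section 4.11 is background, and no operative section schedules a third biopsy. That is also fair, so a one-line confirmation is enough.

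**Conclusion.** The concern holds. The claim of at least 80% power to "detect a moderate correlation of 0.4" is not met at any enrolment figure in the documents. At the cap of 25 the power is 0.51–0.53 for Pearson and about 0.47–0.50 for Spearman. These are favourable figures: they assume that all 25 patients give usable marker and outcome data, that the variables are bivariate normal, and that nothing is adjusted for the many markers listed.

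The 8.2 totals separately imply 46 patients and conflict with the cap. That 46 is also where exact power reaches 0.80 suggests both figures came from a larger design, but the documents do not say so and the conclusion does not depend on it. The text should be corrected; the efficacy conclusion of the trial is unaffected.

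**What to change.** In section 9.6, replace the power sentence with text such as:

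> With at most 25 patients there is about 51% power (Pearson, Fisher z, bivariate normality, two-sided 0.05) to detect a correlation of 0.4; 80% power is reached only for a correlation of about 0.54. If, for illustration, 21 patients are analysable, these become about 44% and 0.58. These figures do not apply directly to the ordinal-response or time-to-event models.

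Deleting the power claim and stating the expected interval width at 25 patients would also be acceptable.

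In section 8.2, restate the biopsy maximum as 25 × 2 = 50, and confirm that the wording in section 4.11, "This study incorporates serial tissues samples pre- treatment, during therapy, and at progression", does not add a third biopsy. Decide which blood schedule applies, align sections 8.1 and 8.2 with the study calendar, and only then restate the blood total.

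The cost is wording in two sections and one decision on the blood schedule. The stated power becomes less favourable. No patients are added and the primary analysis is unchanged.
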